13.3. Other safety monitoring

Adverse events and serious adverse events reported outside of the paper diary card are recorded and reported as described in Section 14.

A placebo controlled clinical trial investigating the safety and immunogenicity of GBS6 in pregnant women with and without human immunodeficiency virus (HIV) infection and their infants

Protocol Version 5.0, Dated 01/02/2023

Protocol Version/date 5.0,01/02/2023

R&D Protocol Code Number:

Page:94

14. Adverse event reporting

For maternal immunisation- clinical studies conducted in pregnant women, data on the exposure during pregnancy (EDP) as well as pregnancy outcome are collected and analysed in the clinical database. For these studies, in general, EDP cases are not reportable unless associated with SAEs/nonserious AEs.

14.1. Requirements

For all AEs, the investigator will pursue and obtain information adequate both to determine the outcome of the AE and to assess whether it meets the criteria for classification as a serious adverse event (SAE) requiring immediate notification to the Makerere University School of Medicine Research and Ethics Committee (SOMREC), Data and Safety Monitoring Board (DSMB), sponsor (SGUL), Uganda National Council for Science and Technology (UNCST) and Pfizer Safety. SAEs shall be reported for the entire duration of the study. Should an investigator be made aware of any SAE occurring any time after the active reporting period, this will be promptly reported.

The table below summarises the requirements for recording safety events on the CRF and for reporting safety events on the Clinical Trial (CT) Serious Adverse Event (SAE) Report Form. These requirements are delineated for the following events: SAEs; non-serious AEs; and occupational exposure.

A placebo controlled clinical trial investigating the safety and immunogenicity of GBSG in pregnant women with and without human immunodeficiency virus (HIV) infection and their infants

Protocol Version 4.0, Dated 11/05/2022

ProtocolVersion/date 5.0, 01/02/2023
R&D Protocol/CodeNumber:
Page:95

Safety Event	Recorded on the CRF	Reported on the CT SAE Report Form Within 24 Hours of Awareness
Maternal and Infant participants		
SAE	All	All
Nonserious AE	All	None
Exposure to the investigational product under study via occupational exposure	None	Occupational exposure (regardless of whether associated with an AE)

The PI/Designee will coordinate the safety monitoring and reporting in the study. SAEs will be reported to SOMREC following local law and requirements. SAEs will be reported to the

A placebo controlled clinical trial investigating the safety and immunogenicity of GBS6 in pregnant women with and without human immunodeficiency virus (HIV) infection and their infants

Protocol Version 4.0, Dated 11/05/2022

ProtocolVersion/date 5.0, 01/02/2023
R&D ProtocolCodeNumber:
Page:96

DSMB as required as well. A detailed description of DSMB functions and responsibilities and guidelines on the transmission flow of SAEs is provided in the DSMB charter. Notification of SAE to concerned National Regulatory Authorities will follow national law requirements. The table below summarizes SAE reporting timelines.

SAE reporting timelines

Reported To	Reported By	Timeline
Sponsor	PI (or designee)	Within 24 hours for all SAEs
Pfizer Safety	PI (or designee)	Within 24 hours for all SAEs
Local IRB	PI (or designee)	As soon as possible but not later than 7 days for all SAEs
Uganda National Drug Authority (NOA)	PI (or designee)	As soon as possible but not later than 7 days for all SAEs
DSMB	Sponsor (or designee)	Within 24 hours for fatal and life threatening events or SUSARs, and within 7 days for other SUSARs (according to DSMB charter)

This time frame also applies to additional new (follow up) information on previously forwarded reports. All SAEs will be monitored

14.2. Additional details on recording adverse events on the CRF

All events detailed in the table above will be recorded on the AE page(s) of the CRF. It should be noted that the CT SAE Report Form for reporting of SAE information is not the same as the AE page of the CRF. When the same data are collected, the forms must be completed in a consistent manner. AEs should be recorded using concise medical terminology and the same AE term should be used on both the CRF and the CT SAE Report Form for reporting of SAE information.

A placebo controlled clinical trial investigating the safety and immunogenicity of GBS6 in pregnant women with and without human immunodeficiency virus (HIV) infection and their infants

Protocol Version 4.0, Dated 11/05/2022

ProtocolVersion/date 5.0, 01/02/2023
R&D Protocol/CodeNumber:
Page:97

14.3. Eliciting Adverse event information

The investigator is to record on the CRF all directly observed AEs and all AEs spontaneously reported by the study participant/parent(s). In addition, each study participant/parent(s) will be questioned about the occurrence of AEs in a nonleading manner.

14.4. Withdrawal from the study due to Adverse events

Withdrawal due to AEs should be distinguished from withdrawal due to other causes, according to the definition of AE noted below, and recorded on the CRF.

When a participant withdraws from the study because of an SAE, the SAE must be recorded on the CRF and reported, as appropriate, on the CT SAE Report Form, in accordance with the Section 14.1, above.

14.5. Time period for collecting AE/SAE information

The period of observation for adverse events extends from the time the study participant receives vaccination until she undergoes the final study examination. Any medical event that occurs after the informed consent form is signed, but prior to being vaccinated and is related to a study procedure, will be documented as an adverse event and recorded on the Adverse Events CRF. Any medical event that occurs after the informed consent form is signed, but prior to being vaccinated and is not related to a study procedure, will be documented as a pre-existing condition and will be recorded on the Medical History CRF. A complete medical history will be noted and physical examination will be performed on all participant before enrolment. The CRFs will capture the medical history and findings of physical examination done at enrolment to establish a baseline. All adverse events, regardless of severity, will be monitored by the investigator until resolution. All participants experiencing adverse events - whether considered associated with the use of the study vaccine or not will be monitored until symptoms subside and any abnormal laboratory values have returned to baseline, or until there is a satisfactory explanation for the changes

A placebo controlled clinical trial investigating the safety and immunogenicity of GBS6 in pregnant women with and without human immunodeficiency virus (HIV) infection and their infants

Protocol Version 4.0, Dated 11/05/2022

ProtocolVersion/date 5.0, 01/02/2023
R&D ProtocolCodeNumber:
Page:98

observed, or until death, in which case a full pathologist's report should be supplied, if possible.

14.5.1 Maternal participants

In this study, the investigator and site staff will ensure the active elicitation and collection of AEs and SAEs through Visit 4. At all subsequent visits (Visits 5 to 9), only MAEs and SAEs, including hospitalisations, will be reported. Immediate AEs will be reported as described in section 13.9.3. In addition, AEs occurring up to 48 hours after the Visit 4, Visit 6 and Visit 9 blood draws that are related to study procedures must be reported in the CRF.

14.5.2 Infant participants

The investigator and site staff will ensure the active elicitation and collection of AEs and SAEs from birth (Infant Visit 1) through Infant Visit 3. At subsequent visits (Visit 4, Visit 5, and Visit 6), only AEs of special interest, MAEs, and SAEs, including hospitalisations, will be reported. In addition, AEs occurring up to 48 hours after the Visit 4 and 6 blood draws that are related to study procedures must be reported in the CRF. In addition, AEs occurring up to 48 hours after the Visit 4 nasal and rectal swab samples that are related to study procedures must be reported in the CRF.

14.5.3 Recording non-serious AEs and SAEs on the CRF

All AEs/SAEs occurring in a participant during the active collection period are recorded in the CRF.

Follow up by the investigator may be required until the event or its sequelae resolve or stabilise at a level acceptable to the investigator, the sponsor and regulatory authorities.

The investigator obtains general information on the pregnancy and its outcome for all study participants. The investigator will follow the pregnancy until completion (or until pregnancy termination). In the case of a live birth, the structural integrity of the neonate can be assessed at the time of birth. In the event of a termination, the reason(s) for termination

A placebo controlled clinical trial investigating the safety and immunogenicity of GBS6 in pregnant women with and without human immunodeficiency virus (HIV) infection and their infants

Protocol Version 4.0, Dated 11/05/2022

ProtocolVersion/date 5.0, 01/02/2023
R&D ProtocolCodeNumber:
Page:99

should be specified and, if clinically possible, the structural integrity of the terminated fetus should be assessed by gross visual inspection (unless pre-procedure test findings are conclusive for a congenital anomaly and the findings are reported).

If the outcome of the pregnancy meets the criteria for an SAE (i.e., ectopic pregnancy, spontaneous abortion, including miscarriage and missed abortion, intrauterine fetal demise, neonatal death [defined as those deaths that occur within 1 month of birth], or congenital anomaly [in a live-born baby, a terminated fetus, an intrauterine fetal demise, or a neonatal death]), the investigator should record this information in the CRF. In addition, infant deaths after 1 month of age should be recorded in the CRF as SAEs.

14.6. Causality assessment

The degree of certainty with which an AE/SAE can be attributed to administration of the study vaccines (or alternative causes, e.g. natural history of the underlying diseases, concomitant therapy, etc.) will be determined by how well the event can be understood in terms of one or more of the following:

- Reaction of similar nature having previously been observed with this vaccine or type of vaccine and/or formulation.
- The event having often been reported in literature for similar types of vaccines.
- The event being temporally associated with vaccination or reproduced on re-vaccination.

[figure not shown]
The Principal Investigator will assess the causality of all AE/SAEs, using the following question: "Is there a reasonable possibility that the AE/SAE may have been caused by the study vaccine(s)?" After assessment of causality, the AE/SAE will be categorized as related or unrelated, as defined below.

Related: there is suspicion that there is a relationship between vaccine and SAE (without determining the extent of probability); there is a reasonable possibility that the vaccine contributed to the SAE. All SAEs assessed as possibly, probably or definitely related to the vaccine

A placebo controlled clinical trial investigating the safety and immunogenicity of GBS6 in pregnant women with and without human Immunodeficiency virus (HIV) infection and their infants

Protocol Version 4.0, Dated 11/05/2022

ProtocolVersion/date 5.0, 01/02/2023
R&D ProtocolCodeNumber:
Page:100

will be considered related to the study product.

Unrelated: there is no suspicion that there is a relationship between vaccine and SAE, there are other more likely causes and administration of the study vaccine is not suspected to have contributed to the SAE. All SAEs assessed as unrelated or doubtfully related to the vaccine will be considered unrelated to the study product.

When assessing AEs/SAEs, the below degree to which an AE/SAE can be attributed to the study vaccines will be used.

Not related: an AE not related to the use of study vaccine

Doubtfully: An AE for which an alternative explanation is more likely e.g. con meds/disease or the relationship in time suggests that a causal relationship is unlikely

Possibly: An AE that might be due to the use of study vaccine. An alternative explanation e.g. con meds/disease is inconclusive. The relationship in time is reasonable, therefore, the causal relationship cannot be excluded.

Probably: An AE that might be due to the use of study vaccine. The relationship in time is suggestive (e.g. confirmed by de-challenge). An alternative explanation e.g. con meds/disease is less likely.

Definitely: An AE that is listed as a possible adverse reaction and cannot be reasonably explained by an alternative explanation e.g. con meds/diseases. The relationship in time is very suggestive (e.g. it is confirmed by de challenge and re-challenge)

14.7. Definition of AE

An adverse event (AE) is defined as any untoward medical occurrence in a subject or clinical investigation subject administered a pharmaceutical product at any dose that does not necessarily have to have a causal relationship with this treatment. An AE can, therefore, be any unfavorable and unintended sign (including an abnormal laboratory finding, for example),

A placebo controlled clinical trial investigating the safety and immunogenicity of GBS6 in pregnant women with and without human immunodeficiency virus (HIV) infection and their infants

Protocol Version 4.0, Dated 11/05/2022

ProtocolVersion/date 5.0, 01/02/2023
R&D ProtocolCodeNumber:
Page:101

MAKERERE UNIVERSITY
SCHOOL OF MEDICINE
APPROVED AMENDMENT
Valid Until
★ 30 NOV 2023 ★
RESEARCH & ETHICS COMMITTEE
[name]

symptom, or disease temporally associated with the use of an investigational product, whether or not considered related to the investigational product. This definition includes intercurrent illnesses or injuries and exacerbation of pre-existing conditions. An unexpected adverse event is one that is not listed in the investigators brochure or current summary of product characteristics or an event that is by nature more specific or more severe than a listed event.

14.7.1 Grading of AEs

Grading of AEs will be undertaken using the criteria below (based on the 2017 DAIDS table)

Grade 1 Mild	asymptomatic or mild symptoms; no or minimal interference with usual social & functional activities, intervention not indicated
Grade 2 Moderate	moderate symptoms causing greater than minimal interference with usual social & functional activities, intervention indicated
Grade 3 Severe	severe symptoms causing inability to perform usual social & functional activities with intervention or hospitalization indicated
Grade 4 Potentially Life-threatening	symptoms causing inability to perform basic self care functions with intervention indicated to prevent permanent impairment, persistent disability or death
Grade 5	Death

14.8. Definition of Serious Adverse Events (SAEs):

An adverse event or suspected adverse reaction is considered "serious" if, in the view of either the investigator or sponsor, it results in any of the following outcomes:

- Life threatening adverse event
- Inpatient hospitalization or prolongation of existing hospitalization

A placebo controlled clinical trial investigating the safety and immunogenicity of GBS6 in pregnant women with and without human immunodeficiency virus (HIV) infection and their infants

Protocol Version 4.0, Dated 11/05/2022

ProtocolVersion/date 5.0, 01/02/2023
R&D ProtocolCodeNumber:
Page:102

MAKERERE UNIVERSITY
SCHOOL OF MEDICINE
APPROVED AMENDMENT
Valid Until

★ 30 NOV 2023 ★

RESEARCH & ETHICS COMMITTEE
[name]

- Persistent or significant incapacity or substantial disruption of the ability to conduct normal life functions
- Congenital anomaly/birth defect
- Important medical events that may not result in death, be life-threatening, or require hospitalization may be considered serious when, based upon appropriate medical judgment, they may jeopardize the patient or subject and may require medical or surgical intervention to prevent one of the outcomes listed in this definition.
- Death

If the outcome of the pregnancy meets the criteria for an SAE (i.e., ectopic pregnancy, spontaneous abortion, including miscarriage and missed abortion, intrauterine fetal demise, neonatal death [defined as those deaths that occur within 1 month of birth], or congenital anomaly [defined as structural or functional anomalies (e.g., metabolic disorders) that occur during intrauterine life and can be identified prenatally, at birth or later in life]). These SAEs can occur in a live-born baby, a terminated fetus, an intrauterine fetal demise, or a neonatal death; the investigator should follow the procedures for reporting SAEs and record this information in the CRF. In addition, any infant death after 1 month of age should be reported as an SAE if the investigator assesses the infant death as related or possibly related to exposure to the investigational product.

Further follow-up may be requested by the sponsor and will be handled on a case-by-case basis (e.g., follow-up on preterm infant participants to identify developmental delays). SAEs occurring in a participant after the active collection period has ended are reported if the investigator becomes aware of them; at a minimum, all SAEs that the investigator believes have at least a reasonable possibility of being related to investigational product must be reported.

A placebo controlled clinical trial investigating the safety and immunogenicity of GBS6 in pregnant women with and without human immunodeficiency virus (HIV) infection and their infants

Protocol Version 4.0, Dated 11/05/2022

ProtocolVersion/date 5.0, 01/02/2023
R&D ProtocolCodeNumber:
Page:103

The same is applied for those SAEs after the active collection period has ended should they occur to the fetus. In addition, infant deaths that occur after 12 months of age should be reported as SAEs when the investigator believes the death has at least a reasonable possibility of being related to investigational product.

Adverse events which do not fall into these categories are defined as non-serious. It should be noted that a severe adverse event need not be serious in nature and that a serious adverse event need not, by definition, be severe.

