4.4. The burden of HIV infection in pregnancy

Globally, almost 1,000 young women are newly infected with HIV daily. In 2013, 1.5 million HIV-infected women worldwide gave birth and of these approximately 60% had access to antiretroviral therapy (ART) ¹⁵. In the era of widespread ART, the vast majority of infants born to HIV infected women are exposed to HIV but uninfected (HEU) leading to a dramatic increase in the absolute number of HEU infants. HEU infants are exposed in utero to HIV particles that might have an effect on their immunologic functions ¹⁶. This immune dysfunction is thought to place the vulnerable HEU at increased risk for infectious diseases mortality and morbidity ¹⁶. HEU infants appear to be at greater risk of GBS disease than their HIV unexposed peers ¹⁷. This could be partially due to the reduced transfer of antibodies across the placenta resulting in lower infant antibody concentrations that wane rapidly, a phenomenon noted in HEU infants for several vaccine-preventable diseases (e.g. *Haemophilus influenzae type B*, acellular pertussis, tetanus) ¹⁸. Uganda is a country with a high pregnancy rate (189 per 1000 women age 15-44), infant mortality (38/1000 livebirths) and high HIV rate in pregnant women (7%) ¹⁰.

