5.2 Primary, secondary and exploratory endpoints

Primary endpoints for primary objectives A1 and A2:

- Maternal primary endpoint 1: Occurrence of solicited local reactions within 7 days following administration of investigational product (pain at the injection site, redness, and swelling).
- Maternal primary endpoint 2: Occurrence of solicited systemic events within 7 days following administration of investigational product (fever, nausea/vomiting, diarrhoea, headache, fatigue/tiredness, muscle pain, and joint pain).
- Maternal primary endpoint 3: Occurrence of solicited and unsolicited adverse events through 1 month after administration of investigational product.
- Maternal primary endpoint 4: Occurrence of SAEs, MAEs, and obstetric complications (peripartum, intrapartum, and postpartum) throughout the study (Visit 1 through the 12month post-delivery study visit) and any unsolicited events leading to study withdrawal.
- Infant primary endpoint 1: Occurrence of unsolicited adverse events from birth to 6 weeks of age

A placebo controlled clinical trial investigating the safety and immunogenicity of GBS6 in pregnant women with and without human immunodeficiency virus (HIV) infection and their infants

Protocol Version 5.0, Dated 01/02/2023

Protocol Version/date 5.0,01/02/2023
R&D Protocol Code Number:
Page:28

- Infant primary endpoint 2: Occurrence of SAEs, AEs of special interest (major congenital anomalies, developmental delay, and suspected or confirmed GBS infection), and MAEs through 12 months of age and any unsolicited events leading to study withdrawal.

Secondary endpoints for secondary objectives B1, B2, B3:

- Maternal secondary endpoint 1: GBS serotype- specific IgG antibody titres measured at baseline, 2 weeks, 1 month after vaccination, at delivery and 6 weeks after delivery in HIV positive and HIV negative women.
- Maternal secondary endpoint 2: GBS serotype specific IgG titres measured at baseline, and at delivery in HIV positive and HIV negative women.
- Infant secondary endpoint 1: GBS serotype specific IgG antibody titres in HIV-exposed and unexposed infant participants measured at birth, 18 weeks and 12 months of life.
- Infant secondary endpoint 2: GBS serotype specific IgG titres in HIV-exposed and unexposed infant participants measured at 18 weeks of life.
- Infant secondary endpoint 3: Placental transfer ratio of GBS-specific antibodies in HIV-exposed and unexposed pregnancies.

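### Protocol 14.8 ties SAE reporting of infant deaths after 1 month to relatedness, against its own Death criterion and 14.5.3; separately, 14.5.1 can end maternal AE collection before primary endpoint 3's month is over

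*Protocol*

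**What the plan says.** **Infant deaths.** Protocol 14.8 calls an event serious if, "in the view of either the investigator or sponsor, it results in any of the following outcomes"; the list that follows includes death with no condition attached. Later in 14.8 comes the sentence at issue: "any infant death after 1 month of age should be reported as an SAE if the investigator assesses the infant death as related". A possible relation to the product is enough to meet this condition. A further sentence deals with the time after the study: "infant deaths that occur after 12 months of age should be reported as SAEs when the investigator believes" that a link to the product is reasonably possible. Section 14.5.3 sets no condition: "infant deaths after 1 month of age should be recorded in the CRF as SAEs". Section 14.1 states that "SAEs shall be reported for the entire duration of the study", and its table, which covers mothers and infants, has all SAEs recorded and all reported. Section 5.2 gives "Infant primary endpoint 2: Occurrence of SAEs, AEs of special interest" and MAEs through 12 months of age, whatever the cause.

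**Maternal AEs.** Maternal primary endpoint 3 (5.2, analysed in 6.3 as a proportion of women) counts solicited and unsolicited AEs through 1 month after vaccination. Section 14.5.1 has AEs actively collected through Visit 4, which is delivery. After that it takes only MAEs and SAEs, plus procedure-related AEs within 48 hours of certain blood draws. Note a to Table 1 drops the 2-week and 1-month visits if delivery comes first.

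**The concern.** The protocol handles the same infant death in two ways. Under 14.5.3, 14.1 and the Death criterion it is an SAE. Under the later sentence of 14.8, a death judged unrelated need not be reported as one. Section 14.6 groups doubtfully related with unrelated, so the deaths left out are not a trivial set. What is mainly at stake is expedited reporting: 24 hours to the sponsor and Pfizer Safety, and 7 days to the IRB and the national drug authority. All of these clocks start when the event is classed as an SAE. Safety is the primary outcome of this trial, and whether a death is reported should not depend on a site's causality judgement.

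On the maternal side, a woman who delivers within a month of vaccination passes to the reduced collection of 14.5.1 before endpoint 3's window closes. A non-serious AE with no medical visit could then be missed.

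**Working it through.** The protocol gives no figure on this point to reproduce. The first part is a comparison of texts; the numbers show only how much could be exposed.

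**1. Infant deaths after 1 month**

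| Place | Condition on relatedness |
|---|---|
| 14.8, Death in the list of serious outcomes | none |
| 14.5.3, recording in the CRF | none |
| 14.5.2, SAEs at infant Visits 4 to 6 | none |
| 14.1, SAE row of the table | none; all recorded, all reported |
| 14.8, infant death after 1 month | related or possibly related |
| 14.8, infant death after 12 months | reasonable possibility of relation |

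The 12-month sentence already covers the time after follow-up, so the 1-month sentence applies to months 1-12. Reading 14.5.3 as recording and 14.8 as reporting does not remove the conflict, because 14.1 requires both for every SAE.

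Exposure, from infant mortality of 38 per 1000 (4.4), neonatal mortality of 19 per 1000 (4.2) and 300 infants:

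- Deaths at 1-12 months = (38 − 19)/1000 × 300 = 5.7.
- A low-risk cohort will have fewer, by a factor the protocol does not give. Assuming one third: 5.7/3 = 1.9. Assuming one tenth: 5.7/10 = 0.57.
- Poisson chance of at least one death, 1 − exp(−m): 99.7%, 85.0% and 43.4%.

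**2. Maternal AEs**

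Vaccination is allowed up to 35 6/7 weeks. Adding 28 days gives 39 6/7 weeks, so ordinary term births can fall inside the window. Of the 63 permitted vaccination days, 20 leave fewer than 28 days before a delivery at 37 0/7 weeks, 13 before one at 38 0/7, and 6 before one at 39 0/7.

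Share of women affected. Assumptions: vaccination uniform over 27-36 weeks, normally distributed gestation at delivery, and mean = 37 + 1.2816 × SD, so that 10% are preterm as in 6.1. Simulation used 4,000,000 draws among women undelivered at vaccination:

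| SD (weeks) | Mean (weeks) | Deliver before day 28 | Of 300 |
|---|---|---|---|
| 1.5 | 38.92 | 14.1% | 42 |
| 1.8 | 39.31 | 12.2% | 37 |
| 2.0 | 39.56 | 11.2% | 34 |

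With mean 39.3 and SD 1.8, 67% of these deliveries are at 37 weeks or later, and on average 8.5 days of the window remain. A 31-day month raises the share to 15.6% (47 women).

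Effect on endpoint 3. Let S be the share of women with a solicited event on days 1-7. Let u be the share with a non-serious unsolicited AE without medical attendance over 28 days, at constant rate. Both are assumed. The true proportion is 1 − (1 − S)(1 − u); the observed one stops u at delivery. Understatement in percentage points:

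| S | u = 0.1 | u = 0.3 | u = 0.5 |
|---|---|---|---|
| 0.3 | 0.25 | 0.71 | 1.08 |
| 0.5 | 0.18 | 0.51 | 0.77 |
| 0.8 | 0.07 | 0.20 | 0.31 |

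Hand check of the largest cell: the daily rate is ln 2/28 = 0.0248. Then 0.122 × 0.7 × 0.5 × (exp(0.0248 × 8.5) − 1) = 0.122 × 0.7 × 0.5 × 0.234 = 0.010. That is about 1.0 point, slightly below 1.08 because it uses the mean days left.

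**The case against.** **Infant deaths.** The 14.8 sentence says if, not only if. It follows a list of pregnancy outcomes and is worded as an addition, so it could be read as widening that list rather than narrowing the SAE definition. Several unconditional rules stand against it. Many infants who die will already have had a hospitalisation or life-threatening event that is itself a reportable SAE. The DSMB row of the 14.1 timelines, "Within 24 hours for fatal and life threatening events or SUSARs", has no relatedness test for fatal events.

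Part of this stands. Section 14.5.3 governs the CRF, so loss of deaths from infant primary endpoint 2 is less likely than a missed or late expedited report. The mortality figures overstate the number of reports at risk. The additive reading fails, however: if the Death criterion already covers these infants, the condition does nothing. The other unconditional rules make the conflict plainer. The DSMB safeguard is only partly independent, because the sponsor makes that report and learns of the death from the site's SAE report.

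**Maternal AEs.** Section 14.5 observes AEs to the final examination. Table 1 marks AE recording at Visits 1 to 9 in a row separate from MAEs and SAEs. Section 14.3 has observed and spontaneously reported AEs recorded without a time limit. These reduce the loss but do not settle the rule, since the Visit 5 and 6 procedures refer back to Section 14, where 14.5.1 restricts what is collected. The effect is also small beside an exact 95% interval of about ±12 points for 75 women near 50%.

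**Conclusion.** Both parts hold, with unequal weight. The conflict over infant deaths is certain from the text and should be fixed. How many reports it would affect cannot be derived from the protocol; 5.7, 1.9 and 0.6 deaths bound the exposure under the national rates and two assumed reductions.

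The maternal gap is real but minor. It concerns roughly 34-42 of 300 women and an understatement of 0.1-1.1 percentage points, under assumed delivery timing and AE rates. A missed event changes the endpoint only for a woman with no earlier AE. The loss arises in both arms and would bias the comparison only if early delivery differed between them.

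**What to change.** 1. In 14.8, remove the relatedness condition for infant deaths up to 12 months of age, so that the text agrees with its Death criterion, 14.5.3 and 14.1. Leave the existing sentence for deaths after 12 months.
2. In 14.5.1, collect all maternal AEs through Visit 4 or 1 month after vaccination, whichever is later, and ask about them at the existing Visits 5 and 6. State the month in days. Visit 6 opens 35 days after delivery, so it always falls after a 28-31 day month. If the month were read as the Visit 3 window to day 42, a delivery in the first 6 days after vaccination would be an exception (6 + 35 = 41).

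The cost is two sentences in an amendment and matching CRF guidance, with no added visit.
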